#### 7.8.1.2 AE summaries

An overall summary of adverse events will be presented.

The frequency of patients with adverse events will be summarised by treatment, primary system organ class and preferred term. Incidence rates as defined in [Section 7.8.1.7](#) will generally be included.

AEs will also be reported by intensity (without incidence rates). Separate tables will be provided for

- for patients with serious adverse events,
- for patients with drug related serious AEs,
- for patients with AEs leading to discontinuation
- for patients with drug-related AEs.

AEs leading to death will be listed.

The system organ classes will be sorted according to the standard sort order specified by the European Medicines Agency (EMA), preferred terms will be sorted by frequency (within system organ class).

Additionally, the following analyses will be reported in Appendix 16.1.13.1 for disclosure on EudraCT and clinicaltrials.gov:

- Frequency [N(%)] of subjects with non-serious adverse events occurring with incidence in preferred term greater than 5% by treatment,
- Adverse events per arm for disclosure on EudraCT by treatment
- Non-serious adverse events for disclosure on EudraCT by treatment
- Serious adverse events for disclosure on EudraCT by treatment

### 7.8.1.3 Adverse events of special interest (AESIs)

#### Hepatic injury

Hepatic injury AEs will be summarised based on a Standardised MedDRA Query (SMQ) based definition. From SMQ Drug related hepatic disorders (20000006) the following narrow sub-SMQs will be used:

- Narrow sub-SMQ Liver related investigations, signs and symptoms (20000008)
- Narrow sub-SMQ Cholestasis and jaundice of hepatic origin (20000009)
- Narrow sub-SMQ Hepatitis, non-infectious (20000010)
- Narrow sub-SMQ Hepatic failure, fibrosis and cirrhosis and other liver damage-related conditions (20000013)

A table with frequencies of patients with these AEs by treatment, primary SOC and preferred term will be provided. Hepatic injury SAEs based on the above SMQ definition will be presented.

Patients with hepatic injury will be listed.

For presentations on adjudicated hepatic events, refer to [Section 7.8.1.5](#).

#### Acute renal failure

A frequency table of patients with AEs related to acute renal failure by treatment, primary SOC and preferred term will be provided based on the narrow SMQ Acute renal failure (20000003).

SAEs and AEs leading to discontinuation based on the narrow SMQ Acute renal failure (20000003) will be presented.

In addition, frequency tables will be produced for patients with elevated creatinine  $\geq 2$  x baseline and  $> 1$  x upper limit of normal (ULN).

Patients with acute renal failure will be listed.

#### Ketoacidosis

A frequency table of patients with AEs related to ketoacidosis will be presented by treatment, primary SOC and preferred term for investigator reported cases and for the narrow and broad BICMQ definition of diabetic ketoacidosis (DKA).

For presentations on adjudicated events, refer to [Section 7.8.1.5](#)

Patients with DKA based on the broad BICMQ (30000019) or investigator reported ketoacidosis will be listed.

#### 7.8.1.4 Specific AEs

##### Hypoglycaemic events

The investigator will record for each AE whether it represents a hypoglycaemic event and, if so, record additional information to assess the intensity of the hypoglycaemic event. On the basis of this information the hypoglycaemic event will be categorised as follows:

- severe hypoglycaemic episode: event requiring the assistance of another person to actively administer carbohydrate, glucagon or other resuscitative actions
- documented symptomatic hypoglycaemia with a measured plasma glucose concentration  $< 3.0$  mmol/L ( $< 54$  mg/dL): event accompanied by typical symptoms of hypoglycaemia but no need for external assistance
- documented symptomatic hypoglycaemia with a measured plasma glucose concentration  $\geq 3.0$  mmol/L and  $\leq 3.9$  mmol/L ( $\geq 54$  mg/dL and  $\leq 70$  mg/dL): event accompanied by typical symptoms of hypoglycaemia and no assistance required
- symptomatic hypoglycaemia and plasma glucose concentration  $> 3.9$  mmol/L (70 mg/dL)
- symptomatic hypoglycaemia and plasma glucose concentration not measured
- asymptomatic hypoglycaemia: event not accompanied by typical symptoms of hypoglycaemia but with a measured plasma glucose concentration  $\leq 3.9$  mmol/L ( $\leq 70$  mg/dL)

Confirmed hypoglycaemic adverse event are defined as hypoglycaemic adverse events that had a plasma glucose concentration  $\leq 70$  mg/dL or required assistance.

Different tables will be shown for (i) patients with investigator-defined hypoglycaemia, and (ii) patients with confirmed hypoglycaemic adverse events, i.e. hypoglycaemic adverse events that had a plasma glucose concentration  $\leq 70$  mg/dL or required assistance.

Subgroup analyses on confirmed events with respect to DM status at baseline (DM vs non-DM) will be performed.

In addition the number of patients with hypoglycaemia according to SMQ (20000226) will be presented.

Patients with hypoglycaemic events will be listed.

##### Urinary tract infections (UTI) and genital infections

The following additional specific adverse events will also be assessed and be tabulated by treatment group:

- Genital infections (BICMQ “Infections” (30000036) narrow subsearch 1.1 “Genital tract infections predisposed to by glucosuria” (30000038) and investigator assessment)

- UTI (BICMQ “Infections” (30000036) narrow subsearch 2.1 “UTI predisposed by glucosuria” (30000041) and investigator assessment)

Genital infections based on investigator assessment will additionally be summarised by type (fungal balanitis or fungal vulvovaginitis, genital infection other than fungal balanitis or fungal vulvovaginitis), intensity (mild, moderate or severe), how the event was treated (no treatment, therapy assigned and number of antimicrobials needed to treat), whether leading to discontinuation of treatment, and the number of episodes per patient.

UTIs based on investigator assessment will additionally be summarised by intensity (mild, moderate or severe), anatomical location (upper UTI, lower UTI), occurrence of pyelonephritis or urosepsis, how the event was treated (no treatment, therapy assigned and number of antimicrobials needed to treat), whether leading to discontinuation of treatment, and the number of episodes per patient.

Complicated urinary tract infections defined as serious adverse events of BICMQ Infection narrow, subsearch 2.1 “UTI predisposed by glucosuria” (30000041), all events of subsearch 2.1.1 ‘Renal infections predisposed by glucosuria’ (30000042), all events of PT Urosepsis will be presented.

Complicated genital infection: defined as all serious events using the BICMQ Infection narrow subsearch 1.1 ‘Genital tract infections predisposed to by glucosuria’ (30000038) and all event of the subsearch ‘Complicated genital tract infections predisposed to by glucosuria’ (30000129) will also be presented.

Patients with UTIs or genital infections will be listed.

#### Bone fracture events:

Frequency tables of patients with bone fracture by treatment, primary system organ class (SOC) and preferred term will be provided (based on the narrow BICMQ “Bone fractures” (30000008) and investigator reporting).

Investigator reported fractures will be reported overall and separately for each type of fracture (traumatic and non-traumatic).

Separate tables for bone fractures based on the BICMQ, which are serious will be presented.

Patients with bone fractures will be listed.

#### Urinary tract malignancy events:

Urinary tract malignancy will be shown based on the BICMQ ‘Malignancies’ (30000049) – broad sub-search 14.1 ‘Urinary bladder and tract malignancies’ (30000057) and broad sub-search 14.2 ‘Renal malignancies’ (30000103):

Presentation of frequency will be done by treatment, high level term and preferred term.

Patients with urinary tract malignancy will be listed.

#### Volume depletion

Volume depletion will be based on the BICMQ ‘Volume depletion of non-haemorrhagic cause and subsequent hypotension’ – narrow subsearch 2 ‘Volume depletion and hypotension due to dehydration’ (30000090).

A frequency table of patients with volume depletion by treatment, primary SOC and preferred term will be provided.

A separate table for serious volume depletion events will be presented.

Patients with volume depletion will be listed.

For the analysis of laboratory data, refer to [Section 7.8.2](#).

#### Hypotension:

Frequency table of subjects with symptomatic hypotension as defined by the investigator on the eCRF tick box by treatment, primary system organ class and preferred term will be provided.

Symptomatic hypotension episodes will be presented by whether the intensity of diuretic medication was reduced and by whether the intensity of non-diuretic antihypertensive therapy was reduced.

A separate table for symptomatic hypotension events, which are serious, will be presented.

Additionally hypotension by treatment, primary system organ class and preferred term will be provided. Hypotension is defined as preferred terms of the BICMQ ‘Volume depletion of non-haemorrhagic cause and subsequent hypotension’ – narrow sub-search 2 ‘Volume depletion and hypotension due to dehydration’ (30000090) but excluding terms of the narrow subsearch 1 ‘Volume depletion due to dehydration’(30000089).

A separate table for hypotension events, which are serious, will be presented.

Patients with hypotension events will be listed.

#### 7.8.1.5 Events qualifying for external adjudication by the adjudication committee

An independent external CEC regularly reviews events and evaluates whether pre-specified criteria for these adjudication endpoints are met. Details on composition of the CEC, responsibilities and clinical event definitions are provided in the separate CEC Charter.

Adjudication assessments will be incorporated into the database.

Details of the adjudication process are described in the CEC charter.

Hepatic adverse events:

Frequency tables summarising the relatedness and severity will be provided, including a listing showing the trigger events and adjudication results. This will include all adjudicated events up to 30 days after treatment stop.

Ketoacidosis:

Frequency tables showing adjudicated certain ketoacidosis will be provided, including a listing showing the trigger events and adjudication results. This will include all adjudicated events up to 7 days after treatment stop.

7.8.1.6 AEs while patients taking wrong medication

A listing will be provided for AEs that occurred while a patient was taking the wrong study medication.

If such a patient is identified an additional adverse event table that assigns the adverse events to the actual treatment taken will be presented. A patient who took both the assigned treatment and also at least one tablet of the wrong treatment will be counted as at risk in both treatment groups for the respective relevant time. The table will include all adverse events by SOC and PT.

7.8.1.7 Adverse event incidence rates

For AE tables showing patients with events, in addition to the frequency tabulations, time-adjusted adverse event analyses will be performed for all AEs, investigator defined drug-related AEs, AEs leading to discontinuation, serious AEs, and adverse events of special interest by SOC and PT or High-Level Term (HLT) and PT, respectively.

The time at risk in patient years for the on-treatment phase is derived as follows:

Patients with AE:

time at risk (AE) in days = date of start of AE with specified PT/SOC/HLT – study treatment start date + 1

Patients without AE:

time at risk (AE) in days = end date of time at risk – study treatment start date + 1, where end date of time at risk is the minimum of date of last study drug intake + x days and date of death, if applicable.

The standard approach will be x=7 days, but for certain AESIs in addition other approaches will be used.

Total AE-specific time at risk per treatment group is then derived as:

Time at risk (AE) [years] = Sum of time at risk [days] over all patients in a treatment group / 365.25

For 'each row of a table' (e.g. displaying an SOC), time at risk is calculated using start of first AE summarised in this row; e.g. for patient with AE in a specified SOC, time at risk = date of start of AE with specified PT in this SOC – start of study treatment + 1.

The AE incidence rate per 100 patient years will then be calculated as follows:

Incidence rate per 100 patient years (pt-yrs) =  $100 * \text{number of patients with AE} / \text{time at risk (AE) [years]}$ .

In a similar way the time at risk and incidence rate for the post-treatment period is derived. Hereby the start date is the start date of the post-treatment phase instead of the study treatment start date.

For some specific outputs showing number of episodes, event rates will be defined as number of episodes divided by time at risk. Time at risk will be end date of time at risk – study treatment start date + 1, where end date of time at risk is the minimum of date of last study drug intake + x days and date of death, if applicable.

## 7.8.2 Laboratory data

Standard safety tables will not include eGFR or creatinine. Analyses for eGFR and creatinine will be done separately.

For continuous safety laboratory parameters, normalised values will be derived as well as the differences to baseline. The process of normalisation as well as standard analyses for safety laboratory data are described in the BI guidance for the Display and Analysis of Laboratory Data ([BI-KMED-BDS-HTG-0042 \(4\)](#)). All analyses considering multiple of times upper limit of normal (ULN) will be based on original and not normalised data.

Laboratory parameters will be shown in conventional units. Where conventional units differ from SI units, analyses will be repeated on SI units.

The analyses of laboratory data will be descriptive in nature and will be based on BI standards [see Data Management and Statistics Manual (DM&SM): Display and Analysis of Laboratory Data ([BI-KMED-BDS-HTG-0042 \(4\)](#))].

Laboratory measurements taken up to 3 days after the last administration of randomised study drug will be considered as on-treatment.

Default settings will be used for repeated values (using closest and then worst value).

Laboratory values will be compared to their reference ranges and frequency tables will be provided for the number of patients within and outside the reference range at baseline and the last measurement on treatment. Descriptive statistics will be provided by treatment group for baseline, last value on-treatment and for changes from baseline to last value on treatment. For semi-quantitative or categorical laboratory values, shift tables for baseline and last value on treatment will also be provided. Frequency tables will summarise the number of patients with potentially clinically significant abnormalities.

Additionally, for urine ketones a shift table of baseline vs value at visit for each visit will be shown.

For the table on potentially clinically significant abnormalities only patients with at least one available on-treatment value will be included in the analysis of an individual laboratory parameter. Other tables are comparing baseline to on-treatment values and will only include patients with a baseline value and at least one available on-treatment value. All individual data will be presented in listings.

To support analyses of liver-related adverse drug effects, patients with Aspartate transaminase (AST) and/or Alanine transaminase (ALT)  $\geq 3 \times \text{ULN}$  with concomitant or subsequent Total Bilirubin (TBILI)  $\geq 2 \times \text{ULN}$  in a 30 day period after AST/ALT elevation are of special interest. In addition, of these cases, it will be considered whether the alkaline phosphatase (AP) is less than 2 x ULN (maximum value in a 30 day period after AST/ALT elevation) or not. The start of the 30-day time span is triggered by each liver enzyme elevation above the defined thresholds. Patients who fulfil one or two of the criteria for ALT/AST or total bilirubin elevations above and have no information available for the remaining parameter(s) within the 30 day time window will not be listed under “ALT and/or AST  $\geq 3 \times \text{ULN}$  with TBILI  $\geq 2 \times \text{ULN}$ ”.

In addition ALT/AST will be used to investigate elevated liver enzymes:

- ALT/AST  $\geq 3 \times \text{ULN}$
- ALT/AST  $\geq 5 \times \text{ULN}$
- ALT/AST  $\geq 10 \times \text{ULN}$
- ALT/AST  $\geq 20 \times \text{ULN}$

All liver enzyme elevations within 30 days of treatment discontinuation will be shown.

Frequency tables of patients with elevated liver enzymes defined by ALT and/or AST, total bilirubin and AP combinations will be provided. Details on patients with elevated liver enzymes will be listed.

For the following parameters:

- eGFR,
- creatinine (only descriptive),

the time course of changes will be assessed. The analysis will be performed by applying MMRM models to OC-OT data on the treated set. The MMRM models that will be used are specified in [Section 7.6](#). These analyses will be conducted on data before any normalisation. The MMRM analyses will also be shown graphically.

For the following parameters:

- haemoglobin, and
- haematocrit

the change from baseline will be assessed. The analysis will be performed by applying ANCOVA models to OC-OT data on the treated set. The ANCOVA model will include treatment and baseline as fixed effects. These analyses will be conducted on data before any normalisation.

To support analysis of renal function, eGFR throughout the trial will be categorised according to the following Chronic Kidney Disease (CKD) staging ([Table 7.8.2: 1](#)): All calculations for the staging of renal function will be based on the originally measured laboratory values, not on normalised values with BI standard reference ranges.

For the following parameters measured at the follow-up visit, additionally descriptive statistics at baseline, last value on treatment and follow-up will be provided for patients with valid measurements at all three timepoints.

- creatinine
- eGFR
- haematocrit
- haemoglobin

Table 7.8.2: 1 CKD staging

Stage	eGFR (mL/min/1.73m^2)	Description	Label for displays	Additional labels#
1	≥90	Normal or high	≥90	≥90 (CKD 1)
2	60 to <90	Mildly decreased	60 to <90	60 to <90 (CKD 2)
3A	45 to <60	Mildly to moderately decreased	45 to <60	45 to <60 (CKD 3a)
3B	30 to <45	Moderately to severely decreased	30 to <45	30 to <45 (CKD 3b)
4	15 to <30	Severely decreased	15 to <30	15 to <30 (CKD 4)
5	<15	Kidney failure	<15	<15 (CKD 5)

A shift table from baseline to last value on treatment and to minimum value on treatment for eGFR (CKD-EPI)cr will be provided.

### **7.8.3 Vital signs**

Heart rate over time will be summarised descriptively based on OC-OT on the treated set. Descriptive statistics will also be shown graphically.

Additionally descriptive statistics at baseline, last value on treatment and follow-up for patients with valid measurements at all three timepoints will be shown.

### **7.8.4 ECG and physical examination**

Clinically relevant abnormalities found at physical examination will be considered to have already existed prior to signing of informed consent and therefore should be considered baseline conditions instead of adverse events, unless there is good reason to assume that they first appeared after signing of consent.

Outcomes of ECGs will be part of the reporting of medical history or AE reporting. Categorical findings as collected in the eCRF will also be summarised descriptively.

### **7.8.5 Others**

Not applicable

## **9. ADDITIONAL SECTIONS**

### **9.1 REGIONS AND COUNTRIES**

Countries will be assigned to regions, as outlined in [Table 9.1: 1](#).

Table 9.1: 1 Regions and countries

Region	Country
Australia	Australia
Europe	Germany Greece Italy Norway Poland Portugal Spain Sweden
North America	Canada US

## 9.2 DIABETES STATUS AT BASELINE

Patients will be assigned to diabetes status category, as outlined in [Table 9.2:1](#).

Table 9.2: 1 DM at baseline

Diabetes status at baseline	Definiton
DM	
Patients who fulfil one of the following:
 
 
- investigator-reported medical history of diabetes on the medical history page
 
 
OR
 
 
- any pre-treatment HbA1c value <math>\geq 6.5\%</math>
 

Pre-DM	
Patient who fulfil all of the following:
 
 
- investigator reported 'no' for the medical history of diabetes on the medical history page
 
 
AND
 
 
- a pre-treatment HbA1c value of <math>\geq 5.7\%</math> and all pre-treatment HbA1c <math>< 6.5\%</math>
 

Missing	
Patients who fulfil one of the following:
 
 
- missing assessment of history of diabetes on the medical history page AND all pre-treatment HbA1c <math>< 6.5\%</math>
 
 
OR
 
 
- no pre-treatment measurement of HbA1c AND investigator reported 'no' for the medical history of diabetes on the medical history page
 
 
OR
 
 
- no pre-treatment measurement of HbA1c and missing assessment of history of diabetes on the medical history page
 

Non-DM (excl pre-DM)	Patients not meeting the above criteria

### **9.3 DERIVATION OF RESPONDER THRESHOLD FOR KCCQ-TSS AND CHQ-SAS DYSPNEA**

A minimal clinically meaningful within patient-change in scores (i.e. responder threshold) will be estimated from the trial population (both treatment groups pooled) for KCCQ-TSS and CHQ-SAS Dyspnea using the below algorithm. All observed values will be considered in this analysis without imputation of missing values (OC-AD).

#### **Anchor**

The Patient Global Impression of Severity (PGI-S) of Dyspnea and PGI-S of Heart Failure Symptoms will each be used as the primary anchor for the CHQ-SAS Dyspnea scale and KCCQ-TSS, respectively. The Patient Global Impression of Change (PGI-C) of Dyspnea and PGI-C of Heart Failure Symptoms will be considered as secondary anchor scales for the CHQ-SAS Dyspnea scale and KCCQ-TSS, respectively.

A minimal clinically meaningful improvement for each PGI-S scale will be considered to be at least a one category improvement in change from baseline in PGI-S at week 12.

A minimal clinically meaningful improvement for each PGI-C scale will be considered to be at least “a little better” in PGI-C at week 12.

As an ancillary consideration, the distance walked in 6 minutes will be evaluated as a clinical indicator of patient improvement as well. Patients who improve at least 30 meters from baseline in distance walked in 6 minutes will be considered to be clinical responders [[R17-1227](#)] (5).

#### **Responder Threshold**

To determine the threshold of the Patient Reported Outcome (PRO) measure that best identifies patients with minimal clinically meaningful difference as specified above (responders / non-responders), the following procedure will be applied:

A receiver operating characteristic (ROC) curve of change from baseline of the PRO measure will be derived from the logistic regression model with the binary anchor (at least one category improvement in PGI-S Y/N) as dependent variable.

The mean of the cut-offs closest to the balance point (i.e. where sensitivity equals specificity) will be used as the responder threshold for each respective scale’s PRO score.

For further analysis of the key secondary endpoint as defined in [Section 7.5.1.4](#) a patient will be considered a responder if the PRO score is greater than or equal to the response threshold determined by the anchor of one category improvement in corresponding PGI-S questionnaire.

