#### 7.5.1.4 Further exploratory analyses of the key secondary endpoints

A minimal clinically meaningful within-patient change in scores (i.e. responder threshold) will be estimated from the trial population (both treatment groups pooled) for KCCQ-TSS and CHQ-SAS dyspnea as described in [Appendix 9.3](#).

A responder analysis using a chi-square test will be evaluated in addition. The response threshold will be determined as defined in [Appendix 9.3](#).

An empirical cumulative distribution function of descriptive change from baseline to week 12 by treatment group on OC-AD on the randomised set will be shown.

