## Graphical presentations

The ROC curve will be used to illustrate the ability of the PRO score to discriminate between responders and non-responders. The area under the ROC curve (AUC) will be reported in addition.

Descriptive empirical cumulative distribution functions (ECDF) will also be plotted by each anchors categories for each PRO.

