## Supportive Analyses

Distribution-based analyses will be performed for the CHQ-SAS Dyspnea scale and the KCCQ-TSS on data of change from baseline to week 12 to support the responder definition as defined above.

One standard error of measurement (SEM) as well as  $0.2*SD$  and  $0.5*SD$  of the CHQ-SAS Dyspnea scale and the KCCQ-TSS baseline measurement will be used as benchmarks [R07-1182](6).

The SEM is defined as  $SD * \sqrt{(1 - r)}$  with reliability coefficient  $r=0.88$  for the KCCQ-TSS (Cronbach's alpha in [R17-2666] (7)) and  $r=0.91$  for the CHQ-SAS Dyspnea (Cronbach's alpha in [R17-2917] (8)).

For patients who achieved a one-category improvement in PGI-S Dyspnea at week 12 from baseline, the descriptive median (with inter-quartile range) of CHQ-SAS Dyspnea will be displayed by baseline PGI-S Dyspnea category. The table will be repeated separately for one-category deterioration, two-category improvement, two category deterioration, and no change in PGI-S dyspnea.

For patients who achieved a one-category improvement in PGI-S in heart failure symptoms at week 12 from baseline, the median (with inter-quartile range) of KCCQ-TSS will be displayed by baseline PGI-S in heart failure symptoms category. The table will be repeated for one-category deterioration, two-category improvement, two category deterioration, and no change in PGI-S in heart failure symptoms.

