#### 10. Clinical Summary Score

The Clinical Summary Score is defined as the mean of the following available summary scores:

Physical Limitation Score and Total Symptom Score

Note: references to “means of questions actually answered” imply the following.

If there are n questions in a scale, and the subject must answer m to score the scale, but the subject answers only n-i, where  $n-i \geq m$ , calculate the mean of those questions as

$(\text{sum of the responses to those } n-i \text{ questions}) / (n-i)$

not

(sum of the responses to those n-i questions) / n

The change from baseline to week 12 in KCCQ-TSS will be calculated as the difference of the score at follow-up (week 12) and at baseline.

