#### **9.4.2 Chronic Heart Failure Questionnaire (CHQ) Self-Administered Standardised format (SAS)**

The CHQ-SAS dyspnea score is defined as the mean of Questions 1-5 within the CHQ-SAS.

The CHQ-SAS fatigue score is defined as the mean of question 7, 9, 12, 14.

The CHQ-SAS emotional function score is defined as the mean of questions 6, 8, 10, 11, 13, 15, 16.

The scores for each question of each dimension are added together and divided by the number of questions. Only items that are answered will be scored. That is items that are scored as “not done” or missing will not be included in the summary (average) score. The average score of the completed items will be reported.

The change in the score of each domain will be calculated as the difference of the mean score at follow-up (week 12) and baseline.

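### SAP 9.3 derives the responder threshold on change from baseline, but the sentence that classifies patients compares the score itself with it

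*SAP*

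**What the plan says.** SAP 9.3 introduces the threshold as a change: "A minimal clinically meaningful within patient-change in scores (i.e. responder threshold) will be estimated from the trial population". SAP 7.5.1.4 describes it in the same way. Under the Responder Threshold subheading the derivation also works on change: "A receiver operating characteristic (ROC) curve of change from baseline of the PRO measure will be derived from the logistic regression model". The binary anchor is an improvement of at least one PGI-S category, and the cut-off is taken where sensitivity and specificity balance.

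The classification that follows reads: "a patient will be considered a responder if the PRO score is greater than or equal to the response threshold". It names neither a change nor a visit.

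The neighbouring text bears on what is meant:

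- Under Graphical presentations, the same ROC curve is to "illustrate the ability of the PRO score to discriminate between responders and non-responders".
- Under Supportive Analyses, the distribution-based work is done "on data of change from baseline to week 12 to support the responder definition as defined above".
- SAP 9.4 treats score and change in score as two quantities. For the KCCQ: "The change from baseline to week 12 in KCCQ-TSS will be calculated as the difference of the score at follow-up". For the CHQ-SAS: "The change in the score of each domain will be calculated as the difference of the mean score at follow-up (week 12) and baseline".

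SAP 7.5.1.4 is where the result is used: "A responder analysis using a chi-square test will be evaluated in addition". For the threshold it sends the reader to Appendix 9.3.

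**The concern.** A cut-off found on one variable is applied, as worded, to another. SAP 9.3 is the only place where the comparison behind the SAP 7.5.1.4 chi-square test is written out, and no section defines the PRO score as a change. SAP 5.3 shows the clear form for its own fixed domain thresholds, which it states as an improvement of at least 5 points (KCCQ) or 0.5 points (CHQ).

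If the sentence were programmed as it stands, response would mean a high enough score at week 12, whatever the patient's baseline. Patients who deteriorated could be counted as responders, and the contrast between arms could shrink or vanish.

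**Working it through.** The plan states no threshold value, because the threshold is estimated from trial data. There is therefore no figure to reproduce. The check is textual first, then arithmetical. The classifying sentence names no visit, so week 12 is taken from the context.

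**1. Which variable each step uses**

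| Step (SAP) | Variable named |
|---|---|
| Definition of threshold (7.5.1.4, 9.3) | within-patient change |
| ROC curve (9.3) | change from baseline |
| Supportive analyses (9.3) | change from baseline to week 12 |
| Classification of patients (9.3) | PRO score |

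**2. How the two rules relate**

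Let B be baseline, W the week-12 score, C = W − B the change, and t the threshold. Then W ≥ t is the same as C ≥ t − B. SAP 6.6.2 gives ranges of 0 to 100 for KCCQ-TSS and 1 to 7 for CHQ-SAS dyspnea, so B is never negative. Hence C ≥ t implies W ≥ t. The literal rule misses no true responder and adds every patient whose change lies from t − B up to, but not including, t.

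**3. CHQ-SAS dyspnea, all complete scores**

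The score is the mean of five items rated 1 to 7 (SAP 9.4.2). With all five answered it takes 31 values, 1.0 to 7.0 in steps of 0.2, giving 31 × 31 = 961 baseline/week-12 pairs. Of these, 31 × 30 / 2 = 465 are worsenings.

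| t | Literal responders | Change responders | Disagree | Worsened pairs called responders |
|---|---|---|---|---|
| 0.5 | 961 | 406 | 555 | 465 |
| 1.0 | 961 | 351 | 610 | 465 |
| 1.5 | 868 | 276 | 592 | 378 |
| 2.0 | 806 | 231 | 575 | 325 |

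For example, at t = 1.5 the scores 1.0, 1.2 and 1.4 fail the literal rule, so 28 × 31 = 868 pairs pass. The change rule needs at least 8 steps of 0.2, so 23 × 24 / 2 = 276 pairs pass, and 868 − 276 = 592. A patient who falls from 4.0 to 1.6 (change −2.4) is then a literal responder.

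**4. Who is left as a non-responder at thresholds of 0.5 and 5**

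These two values are borrowed from the domain responders in SAP 5.3.

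- CHQ: of 7^5 = 16,807 answer patterns, 0 have a mean below 0.5.
- KCCQ-TSS: under the SAP 9.4.1 scoring there are 5 × 7 × 7 × 5 × 5 × 5 × 5 = 153,125 complete patterns. One step up from the worst answer adds 3.125 points (questions 3, 9), 2.083 (questions 5, 7) or 4.167 (questions 4, 6, 8). Totals below 5 come from no step (1 pattern), one step (2 + 2 + 3 = 7) and two steps within questions 5 and 7 (3), which makes 11 patterns.

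Pair and pattern counts are not proportions of patients.

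**5. Size of the lost contrast**

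Inputs are the Protocol 7.7.1 planning values: a 0.5-point effect with SD 1 to 1.4 for CHQ, and a 5-point effect with SD 13 to 20 for KCCQ-TSS. Assumptions are thresholds of 0.5 and 5, normal changes, the KCCQ SD taken as an SD of change, and placebo mean changes of 0 to 0.5 (CHQ) and 0 to 5 (KCCQ-TSS).

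The responder share is 1 − Φ((t − mean change)/SD). For CHQ with SD 1.2 and placebo mean 0.25:

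- Placebo: 1 − Φ((0.5 − 0.25)/1.2) = 41.7%
- Empagliflozin: 1 − Φ((0.5 − 0.75)/1.2) = 58.3%
- Difference: about 16.5 points

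Differences in percentage points over the assumed placebo means:

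| Scale | SD | Change rule |
|---|---|---|
| CHQ | 1.0 | 19.1–19.7 |
| CHQ | 1.2 | 16.2–16.5 |
| CHQ | 1.4 | 14.0–14.2 |
| KCCQ-TSS | 13 | 15.0–15.2 |
| KCCQ-TSS | 15 | 13.1–13.2 |
| KCCQ-TSS | 17 | 11.6–11.7 |
| KCCQ-TSS | 20 | 9.9 |

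Under the literal rule the CHQ difference is 0 (100% against 100%). For KCCQ-TSS, if week-12 scores had mean 50 to 70 and SD 20 to 25 (not in the documents), the literal rule would class about 96% to 99.9% as responders at a threshold of 5.

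**The case against.** The strongest reply is that context already settles the matter. Both SAP 7.5.1.4 and the opening of 9.3 call the threshold a change, the ROC curve is built on change, and the supportive analyses tie the responder definition to change data. SAP 9.3 also uses the PRO score as loose shorthand for the ROC variable, both in the cut-off sentence and under Graphical presentations. On this view the sentence is incomplete rather than wrong: to read it as a week-12 level one supplies the missing visit from context while declining to supply the missing change. The analysis is exploratory, and a table showing 100% responders would be caught at output review.

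Most of this stands. Change is clearly intended, and an attentive programmer would probably use it. The objection does not remove the defect, because the shorthand is never defined and SAP 9.4 defines score and change separately. Nor would output review catch every case: with a CHQ threshold above 1, or for KCCQ-TSS, the result would be a high responder rate and not an impossible one.

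**Conclusion.** The concern holds, as a minor wording error. The sentence omits that the change from baseline is what is compared with the threshold and, followed literally, misclassifies in one direction only, by adding responders. That direction, and the 100% CHQ response at any threshold of 1 or less, follow from the score ranges alone. The percentage-point losses depend on the assumed thresholds, normality and planning SDs, and the conclusion does not need them.

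The reach is narrow. Only the chi-square responder analysis of the two key secondary endpoints is exposed. The primary Wilcoxon test, the Hochberg step, the sample size and the fixed-threshold domain responders in SAP 5.3 and 7.6.1 are unaffected.

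**What to change.** In the classifying sentence of SAP 9.3 (Responder Threshold), replace the bare reference to the PRO score with *the change from baseline to week 12 in the PRO score*, and leave the rest of the sentence as it is. This alone removes the error. It is sensible, though optional, to use the same wording in the cut-off sentence of that subsection and under Graphical presentations, so that SAP 9.3 names one variable throughout.

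The cost is one phrase, or three if all uses are aligned. It needs no new data, adds no analysis choice beyond what SAP 7.5.1.4 and 9.3 already intend, and alters no confirmatory test.
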